2.4.4.3 Multiplicity issues

Multiplicity is considered for performing an interim analysis and for testing multiple endpoints. The overall Type-I error rate will be controlled at the two-sided 0.05 level.

An interim analysis will be performed using the Kim-DeMets (9) spending function when the information fraction is ≥ 0.92 based on follow-up time for the primary endpoint of annualized rate of moderate or severe COPD exacerbations over 52-week treatment period (see [Section 3](#)).

A hierarchical testing procedure will be used for testing primary, key secondary and other endpoints. If the primary endpoint does not demonstrate efficacy at this interim analysis then the study will remain blinded and the primary endpoint will be retested at the 52-week final analysis time point with an $\alpha=0.049$. If the primary endpoint demonstrates efficacy at this interim analysis based on the alpha allocated, then the rest of the multiplicity-controlled endpoints will be tested with $\alpha=0.05$. The comparisons will be tested based on the hierarchical order below.

1) Primary efficacy endpoints:

- Annualized rate of moderate or severe COPD exacerbations over the 52-week treatment period compared to placebo.

2) Secondary/exploratory efficacy endpoints:

- Change in pre-bronchodilator FEV₁ from baseline to Week 12 compared to placebo
- Change in pre-bronchodilator FEV₁ from baseline to Week 52 compared to placebo
- Change in pre-bronchodilator FEV₁ from baseline to Week 12 compared to placebo in the subgroup of patients with baseline FeNO ≥ 20 ppb
- Change in pre-bronchodilator FEV₁ from baseline to Week 52 compared to placebo in the subgroup of patients with baseline FeNO ≥ 20 ppb
- Change from baseline to Week 52 in SGRQ total score compared to placebo
- Proportion of patients with SGRQ improvement ≥ 4 points at Week 52 compared to placebo
- Change in E-RS COPD total score from baseline to Week 52 compared to placebo
- Annualized rate of moderate or severe COPD exacerbation compared to placebo over the 52-week treatment period in the subgroup of patients with baseline FeNO ≥ 20 ppb

The study is considered positive when the primary endpoint achieves statistical significance.

2.4.4.4 Additional efficacy analyses

2.4.4.4.1 Comparisons for other secondary efficacy endpoints

- Change in pre-bronchodilator FEV₁ from baseline to Weeks other than 12 and 52
- Change in post-bronchodilator FEV₁, forced expiratory flow (FEF) 25-75%, FEV₁/FVC from baseline to Weeks up to Week 52
- Time to first moderate or severe COPD exacerbation compared to placebo during the 52-week treatment period
- Annualized rate of severe COPD exacerbations over the 52-week treatment period

2.4.4.4.2 Analyses of other efficacy endpoints for dupilumab versus placebo up to Week 52

Change from baseline in continuous endpoint (pre-bronchodilator FEV₁, post-bronchodilator FEV₁, FEF25-75%, SGRQ total scores) at all time-points will be analyzed in a similar way as change from baseline in pre-bronchodilator FEV₁ at Week 52. Age, sex and height will be included as covariates only in the models for spirometry parameters. Descriptive statistics including number of patients, mean, standard error, and least squares (LS) means will be provided for all visits. In addition, difference in LS means and the corresponding 95% confidence intervals (CI) will be provided along with the p-values.

Proportion type efficacy endpoints (SGRQ improvement from baseline ≥ 4 points) during the treatment period will be analyzed in a similar way as proportion of patients with SGRQ improvement ≥ 4 points at Week 52, except that the response variable will be the responder status at the corresponding visit instead of at Week 52. Odds ratio of being a responder comparing dupilumab to placebo will be provided along with the corresponding 95% CI and p-value at each visit. Descriptive statistics including number and percentage of responders will also be provided.

Primary estimand for other secondary efficacy endpoints is summarized in Appendix L.

2.4.4.4.3 Analyses of time to first moderate or severe COPD exacerbation compared to placebo during the 52-week treatment period

The time to first moderate or severe COPD exacerbation will be analyzed using a Cox regression model. The model will include the time to the first event as the dependent variable, and treatment group, region (pooled country), ICS dose at baseline (high dose ICS [yes/no]), smoking status at screening (current smokers or not), baseline disease severity (as % predicted post-bronchodilator FEV₁), and number of moderate or severe COPD exacerbation events within one year prior to the study (≤ 2 , 3, or ≥ 4) as covariates. Hazard ratio and corresponding 95% CI and p values will be estimated for dupilumab versus placebo. The Kaplan-Meier method will be used to derive the probabilities that a patient would experience an event up to specific timepoints for each treatment group. Kaplan-Meier curves will be generated; point probabilities will be calculated. Interval estimates will be calculated using 95% point wise confidence intervals.

2.4.4.4.4 Analyses of annualized rate of severe COPD exacerbations over the 52-week treatment period

The annualized event rate of severe COPD exacerbations will be analyzed in the same way as the primary analysis for the annualized rate of moderate or severe COPD exacerbation events. The estimated event rate for each treatment group and its two-sided 95% confidence intervals will be provided. The event rate ratio of dupilumab against placebo, two-sided 95% confidence intervals of the rate ratio and the corresponding p-value will also be provided.

2.4.4.4.5 Additional subgroup analyses by smoking status

Additional analyses based on smoking status at screening (current smokers, former smokers) will be performed other than the subgroup analyses specified in [Section 2.4.4.1](#) and [Section 2.4.4.2](#). In each subgroup (current smokers, former smokers), the endpoints will be analyzed using the same primary analysis approach for their corresponding endpoints in the total population.

- For continuous endpoints, descriptive statistics including number of patients, mean, standard error, and least squares (LS) means for each subgroup will be provided. In addition, difference in LS means and the corresponding 95% confidence intervals (CI) will be provided for each subgroup.
- For proportion type endpoints, odds ratio of being a responder comparing dupilumab to placebo will be provided for each subgroup along with the corresponding 95% CI and p-value. Descriptive statistics including number and percentage of responders will also be provided for each subgroup.
- For time to event endpoints, hazard ratio and corresponding 95% CI and p values will be estimated for dupilumab versus placebo for each subgroup. The Kaplan-Meier method will be used to derive the probabilities that a patient would experience an event up to specific timepoints for each treatment group within the subgroup. Kaplan-Meier curves will be generated; point probabilities will be calculated. Interval estimates will be calculated using 95% point wise confidence intervals.

2.4.4.5 Analyses of exploratory efficacy endpoints

2.4.4.5.1 Analyses of other continuous endpoints

- For post-bronchodilator FEV₁, the rate of change in FEV₁ (termed as FEV₁ slope) will be compared between dupilumab against placebo. Repeated post-bronchodilator FEV₁ after Week 4 and after Week 8 up to Week 52 will be analyzed correspondingly using linear mixed-effects model with treatment, age, sex, height, region (pooled country), ICS dose at baseline (high dose ICS [yes/no]), smoking status at screening (current smokers or not), time since randomization, and treatment-by-time interaction and baseline post-bronchodilator FEV₁ as covariates. Intercept and time since randomization are random effects. Individual post-BD FEV₁ slope will be calculated as the slope of a linear regression model with the post-BD FEV₁ (L) at each visit as the response variable and the time since randomization as the independent variable. Descriptive statistics including number of patients, mean, standard error of the individual post BD FEV₁ slopes will be provided. Estimated from the linear mixed-effects model, least squares (LS) means,

difference in LS means and the corresponding 95% confidence intervals (CI) will also be provided.

- Change from baseline in FVC (percent predicted and absolute change in ml), weekly E-RS symptom scores at all time-points will be analyzed in a similar way as change from baseline in pre-bronchodilator FEV₁ at Week 52. Age, sex and height will be included as covariates only in the models for spirometry parameters. Descriptive statistics including number of patients, mean, standard error, and least squares (LS) means will be provided. In addition, difference in LS means and the corresponding 95% confidence intervals (CI) will be provided.
- Change from baseline in BODE index score at Week 52 will be analyzed using the ANCOVA model with the following covariates: treatment group, region (pooled country), ICS dose at baseline (high dose ICS [yes/no]), smoking status at screening (current smokers or not), and baseline BODE index score. Descriptive statistics including number of patients, mean, standard error, and least squares (LS) means will be provided. In addition, difference in LS means and the corresponding 95% confidence intervals (CI) will be provided.
- EQ-5D-5L single index and EQ visual analog scale score will be analyzed using MMRM model with the following covariates: treatment group, region (pooled country), ICS dose at baseline (high dose ICS [yes/no]), smoking status at screening (current smokers or not), visit, treatment-by-visit interaction, baseline EQ-5D-5L single index (or EQ visual analog scale score), and corresponding baseline-by-visit interaction. Descriptive statistics including number of patients, mean, standard error, and least squares (LS) means will be provided. In addition, difference in LS means and the corresponding 95% confidence intervals (CI) will be provided.

2.4.4.5.2 Analyses of time to first severe COPD exacerbation compared to placebo during the 52-week treatment period

The time to first severe COPD exacerbation will be analyzed using the same approach as that for the analyses of time to first moderate or severe COPD exacerbation compared to placebo during the 52-week treatment period. Hazard ratio and corresponding 95% CI and p values will be estimated for dupilumab versus placebo. The Kaplan-Meier method will be used to derive the probabilities that a patient would experience an event up to specific timepoints for each treatment group. Kaplan-Meier curves will be generated; point probabilities will be calculated. Interval estimates will be calculated using 95% point wise confidence intervals.

2.4.4.5.3 Analyses of COPD exacerbation utilizing the Exacerbations of Chronic Pulmonary Disease Tool (EXACT)

COPD exacerbation will be derived using EXACT method as specified in the Exacerbations of Chronic Pulmonary Disease Tool (EXACT) Patient-Reported Outcome (PRO) User Manual-Scoring guide (Version 8.0), March 2016.

The annualized event rate of COPD exacerbations assessed by the EXACT over 52 weeks (a tertiary/exploratory endpoint) will be analyzed in the same way as the primary analysis for the

annualized rate of moderate or severe COPD exacerbation events but based on exacerbation defined by EXACT method instead of the adjudicated data of AECOPD page in eCRF. The estimated event rate for each treatment group and its two-sided 95% confidence intervals will be provided. The event rate ratio of dupilumab against placebo, two-sided 95% confidence intervals of the rate ratio will also be provided.

2.4.4.5.4 Analyses of controller medication change after exacerbation

Increase in number of controller medication and/or total daily dose after adjudicated exacerbation during the treatment period will respectively be summarized by treatment group in terms of number of exacerbation events. For patients who discontinue treatment, data collected during the off-treatment period will also be used. Descriptive statistics including number, mean, median, standard deviation, min, and max will be provided, and no statistical testing will be conducted.

2.4.4.6 Missing data handling

For all continuous efficacy endpoints, the details of missing data handling are described in [Section 2.4.4.1](#).

For responder type endpoints, the details of missing data handling are described in [Section 2.4.4.2](#).

In addition, the reason and pattern of missing data will be carefully examined and pattern mixture modeling approach and other sensitivity analyses will also be performed as specified in [Section 2.4.4.1](#).

2.4.5 Analyses of safety data

The summary of safety results will be presented by treatment group. All safety data collected up to the primary analysis cut-off date (either the IA cut-off date or cut-off date when last patient completes Week 52) will be included.

General common rules

All safety analyses will be performed on the safety population as defined in [Section 2.3.2](#), unless otherwise specified, using the following common rules:

- The baseline value is defined as the last available value before the first dose of IMP.
- The potentially clinically significant abnormality (PCSA) values are defined as abnormal values considered medically important by the Sponsor according to predefined criteria/thresholds based on literature review and defined by the Sponsor for clinical laboratory tests and vital signs and ECG [Appendix A]
- PCSA criteria will determine which patients had at least 1 PCSA during the treatment-emergent adverse event period, taking into account all evaluations performed during the treatment-emergent adverse event period, including nonscheduled or repeated evaluations. The number of all such patients will be the numerator for the on-treatment PCSA percentage

- The treatment-emergent PCSA denominator by group for a given parameter will be based on the number of patients assessed for that given parameter in the treatment-emergent adverse event period by treatment group on the safety population.
- For quantitative safety parameters based on central laboratory/reading measurements, descriptive statistics will be used to summarize results and change from baseline values by visit and treatment group. Summaries will include the endpoint value and/or the worst on-treatment value. The endpoint value is commonly defined as the value collected at the end of treatment. If this value is missing, this endpoint value will be the closest value prior to the end of treatment epoch. The worst value is defined as the nadir and /or the peak post-baseline (up to the end of treatment epoch or EOT) according to the direction (minimum or maximum) of the abnormality as defined in the PCSA list
- The analysis of the safety variables will be essentially descriptive and no systematic testing is planned. Relative risks versus placebo and their 95% confidence intervals may be provided, if relevant
- All safety values including unscheduled measurements will be assigned to the appropriate safety analysis visit window defined in [Section 2.5.3](#).

2.4.5.1 Analyses of adverse events

Generalities

The primary focus of adverse event reporting will be on treatment-emergent adverse events. Pretreatment and posttreatment adverse events will be described separately.

If an adverse event date/time of onset (occurrence, worsening, or becoming serious) is incomplete, an imputation algorithm will be used to classify the adverse event as pretreatment, treatment-emergent, or posttreatment. The algorithm for imputing date/time of onset will be conservative and will classify an adverse event as treatment emergent unless there is definitive information to determine it is pretreatment or posttreatment. Details on classification of adverse events with missing or partial onset dates are provided in [Section 2.5.2](#).

Adverse event incidence tables will present by SOC, HLT, HLT, and PT, sorted in alphabetical order for each treatment group, the number (n) and percentage (%) of patients experiencing an adverse event. Multiple occurrences of the same event in the same patient will be counted only once in the tables within a treatment phase. The denominator for computation of percentages is the safety population within each treatment group.

Sorting within tables ensures the same presentation for the set of all adverse events within the observation period (pretreatment, treatment-emergent, and posttreatment). For that purpose, the table of all treatment-emergent adverse events presented by SOC and PT sorted by the internationally agreed SOC order and decreasing frequency of PTs within SOCs will define the presentation order for all other tables unless otherwise specified. Sorting will be based on results for the dupilumab 300 mg q2w group.

Risk differences (constructed using the Miettinen and Nurminen method) and hazard ratios (Cox proportional hazards model) for dupilumab versus placebo with corresponding 95% CIs will be provided for the overview table, common TEAEs (PT $\geq 1\%$, 2%, 5% in any intervention

group), and AESIs and other selected AE grouping events table. Participants without an event will be censored at the end of the treatment-emergent period in the Cox model. Forest plots will also be presented.

Analysis of all treatment-emergent adverse events

The following treatment-emergent adverse event summaries will be generated for the safety population.

- Overview of treatment-emergent adverse events, summarizing number (%) of patients with any:
 - Treatment-emergent adverse event
 - Serious treatment-emergent adverse event
 - Treatment-emergent adverse event leading to death
 - Treatment-emergent adverse event leading to permanent treatment discontinuation
- All treatment-emergent adverse event by primary SOC, HLGT, HLT, and PT, showing number (%) of patients with at least 1 treatment-emergent adverse event sorted by the SOC internationally agreed order. The other levels (HLGT, HLT, PT) will be presented in alphabetical order.
- Number (%) of patients experiencing TEAE(s) presented by PT, sorted by decreasing incidence of PT.
- All treatment-emergent adverse events by primary SOC and PT, showing the number (%) of patients with at least 1 treatment-emergent adverse event, sorted by the internationally agreed SOC order and by decreasing incidence of PTs within each SOC in the 300 q2w treatment group.
- All treatment-emergent adverse events regardless of relationship and related by primary SOC, HLGT, HLT and PT, showing the number (%) of patients with at least 1 treatment-emergent adverse event, sorted by the internationally agreed SOC order. The other levels (HLGT, HLT, PT) will be presented in alphabetical order.
- All treatment-emergent adverse events by maximal severity, presented by primary SOC and PT, showing the number (%) of patients with at least 1 treatment-emergent adverse event by severity (ie, mild, moderate, or severe), sorted by the internationally agreed SOC order and by decreasing incidence of PTs within each SOC in the 300 q2w treatment group.
- Number (%) of patients experiencing treatment-emergent adverse event(s) presented by primary and secondary SOC, HLGT, HLT, and PT sorted by the internationally agreed SOC order. The other levels (HLGT, HLT, PT) will be presented in alphabetical order.

A listing of all treatment-emergent adverse events will be presented.

Analysis of all treatment emergent serious adverse event(s)

- All treatment-emergent serious adverse events by primary SOC, HLGT, HLT, and PT, showing the number (%) of patients with at least 1 serious treatment-emergent adverse event, sorted by the internationally agreed SOC order. The other levels (HLGT, HLT, PT) will be presented in alphabetical order.

- All treatment-emergent serious adverse events regardless of relationship and related to IMP, by primary SOC, HLT, and PT, showing the number (%) of patients with at least 1 treatment-emergent serious adverse event, sorted by the internationally agreed SOC order. The other levels (HLGT, HLT, PT) will be presented in alphabetical order.
- All treatment-emergent serious adverse events by primary SOC and PT, showing the number (%) of patients with at least 1 treatment-emergent serious adverse event, sorted by the internationally agreed SOC order and by decreasing incidence of PTs within each SOC in the 300 q2w treatment group.

A listing of all treatment-emergent serious adverse events will be presented

Analysis of all treatment-emergent adverse event(s) leading to treatment discontinuation

- All treatment-emergent adverse events leading to treatment discontinuation, by primary SOC, HLT, and PT, showing the number (%) of patients sorted by the internationally agreed SOC order. The other levels (HLGT, HLT, PT) will be presented in alphabetical order.
- All treatment-emergent adverse events leading to permanent treatment discontinuation or drug interruption, by primary SOC and PT, showing number (%) of patients with at least one TEAE, will be presented by SOC internationally agreed order and by decreasing incidence of PTs within each SOC in the 300 q2w treatment group.

Analysis of Major Cardiovascular Adverse Events (MACE)

- The number and percentage (%) of patients with any treatment-emergent event selected for adjudication will be summarized by primary SOC and PT.
- All events submitted for adjudication will be listed, including the final adjudicated result.
- The number and percentage (%) of patients experiencing a treatment-emergent adjudicated event will be summarized within each treatment group.
- The risk difference (asymptotic 95% CI with continuity correction) will be computed for the dupilumab dose versus placebo. Kaplan-Meier plots to depict the course of onset over time will also be provided.

Analysis of adverse events of special interests (AESI)and other selected AE groupings

- All treatment-emergent adverse events, by selected standardized MedDRA query (SMQ) and PT or by laboratory values (as in ALT elevation), showing the number (%) of patients with at least 1 PT, sorted by decreasing incidence of PTs within each SMQ in the 300 q2w treatment group.
- For each AESI and other selected AE groupings,
 - Number (%) of patients with any specific TEAE
 - Number (%) of patients with any specific serious AE (regardless of treatment emergent status)
 - Number (%) of patients with any specific treatment emergent serious AE
 - Number (%) of patients with any specific AE leading to death
 - Number (%) of patients with any specific TEAE leading to permanent study drug discontinuation

- Number (%) of patients with any specific TEAE related to IMP reported by investigator
- Number (%) of patients with any specific TEAE by maximum intensity, corrective treatment, and final outcome
- Number of any specific TEAE adjusted by the exposure duration
- Number of patients with any specific TEAE adjusted by the exposure duration at risk. For each specific TEAE, Kaplan-Meier estimates of cumulative incidence at Week 12, 24, 36 and 52 and K-M plot may be provided to depict the course of onset over time if the number of events is large enough.
- Number (%) of patients with injection site reactions by the related injection.
- Number (%) of patients with different number of injection site reactions.
- In addition, AESIs reported by the investigator in CRF will be summarized separately.

Analysis of pretreatment adverse events

- All pretreatment adverse events by primary SOC and PT, showing the number (%) of patients with at least 1 pretreatment adverse event, sorted by the internationally agreed SOC order and decreasing incidence of PTs within each SOC in the 300 q2w treatment group.
- All serious pretreatment adverse events by primary SOC and PT, showing the number (%) of patients with at least 1 pretreatment adverse event, sorted by the internationally agreed SOC order and decreasing incidence of PTs within each SOC.
- All pretreatment adverse events leading to permanent treatment discontinuation by primary SOC and PT, showing the number (%) of patients, sorted by the internationally agreed SOC order and decreasing incidence of PTs within each SOC.
- All pretreatment adverse events leading to death by primary SOC and PT, showing the number (%) of patients, sorted by the internationally agreed SOC order and decreasing incidence of PTs within each SOC.
- If only a few patients have pretreatment adverse events leading to permanent treatment discontinuation, a listing will be presented instead of the summary table above.

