- a Randomization/baseline visit is defined as Day 1. The visit schedule should be adhered to within ±1 week for the 4-week screening period, ±3 days for the randomized IMP treatment period and ±5 days for the post IMP treatment period. If more than 12 weeks since last on-site scheduled visit, then unscheduled visit is required within 3 weeks of missed scheduled visit (eg, if missed scheduled visit at Week 24, then unscheduled visit must be performed by Week 27; If missed scheduled visit at Week 36, then unscheduled must be performed by Week 39). All the assessments of the missed scheduled on-site visit will need to be carried out at the unscheduled visit.
- b All assessments at Visit 2 (Day 1) are to be conducted pre-IMP dose with the exception of the assessment of local tolerability of SC injections.
- c End-of-treatment visit: See Section 7.1.1 for patients who discontinue treatment prematurely.
- d ECG to be centrally collected & read.
- Chest X-ray to be performed unless a <6-month-old chest x-ray/chest CT/chest MR is available. In case chest-X-ray is not feasible due to local regulations, magnetic resonance imaging (MRI) will be performed.
- f IMP (Dupilumab or placebo) is to be administered every 2 weeks by patient, caregiver or healthcare professional at the patient's home or in a health care facility. Last dose will be given at Week 50. If the patient or Investigator decides not to administer IMP at home, the IMP injections can be performed at the site by way of unscheduled visits. The IMP can be administered at home after training and at least 1 IMP injection at the site and supervised by the Investigator. Patients will be monitored at the study site for a minimum of 30 minutes after injections. See Section 6.1.1 for details. If the patient is unable or unwilling to administer IMP at home, injections can be performed at the site; or arrangements can be made for qualified site personnel and/or health care professionals (eg, visiting nurse service) to administer IMP for the doses that are not scheduled to be given at the study site.

Amended Clinical Trial Protocol 03 EFC15805 - dupilumab

28-Oct-2023 Version number: 1

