9.4.2 Safety analyses

The summary of safety results will be presented by treatment group. All safety analyses will be performed on the Safety Population. The baseline value is defined generally as the last available value before randomization. The treatment emergent adverse event (TEAE) period is defined as the time between the first administration of study medication to the last administration of the IMP +98 days.

Table 10 - Safety analyses

Table 10 - Salety analyses	
Endpoint	Statistical Analysis Methods
AE, SAE, AE leading to death, AE leading to permanent treatment discontinuation.	Adverse event incidence tables will present by system organ class (SOC) (sorted by internationally agreed order), high-level group term (HLGT), high level term (HLT) and preferred term (PT) sorted in alphabetical order for each treatment group, the number (n) and percentage (%) of patients experiencing an AE. Multiple occurrences of the same event in the same patient will be counted only once in the tables within a treatment phase. The denominator for computation of percentages is the safety population within each treatment group. Proportion of patients with at least one TEAE, treatment emergent SAE, TEAE leading to death, and TEAE leading to permanent treatment discontinuation will be tabulated by treatment group. In addition TEAEs will be described according to maximum intensity and relation to the study drug. AEs that occur outside the treatment-emergent period will be summarized separately.
Major Cardiovascular Adverse Events (MACE)	The number and percentage (%) of patients with any treatment-emergent event selected for adjudication will be summarized by primary SOC and PT. All events submitted for adjudication will be listed, including the final adjudicated result. The number and percentage (%) of patients experiencing a treatment-emergent adjudicated event will be summarized within each treatment group. The risk difference (asymptotic 95% CI with continuity correction) will be computed for the dupilumab dose versus placebo. Kaplan-Meier plots to depict the course of onset over time will also be provided.

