2.1.4 Safety endpoints

The safety analysis will be based on the reported adverse events and other safety information, such as clinical laboratory data, vital signs, ECG and physical examination.

Observation period

The observation period will be divided into 4 epochs:

- The **screening** epoch is defined as the time from the signed informed consent date up to the time prior to first administration of the IMP.

- The **treatment** epoch is defined as the time from the first administration of the IMP to the last administration of the IMP + 14 days.
- The **residual treatment** epoch is defined as the time from the last administration of the IMP +15 days to the last administration of the IMP + 98 days.

The treatment-emergent adverse event period will include both **treatment** and **residual treatment** epochs.

- The **posttreatment** epoch is defined as the period of time starting the day after the end of the treatment-emergent adverse event period up to the end of the study (defined as last protocol planned visit or the resolution/stabilization of all serious adverse events and adverse events with pre-specified monitoring).
- The on-study observation period is defined as the time from start of treatment until the end of the study (defined as last protocol planned visit or lost to follow-up or the resolution/stabilization of all serious adverse events and adverse events with pre-specified monitoring).

Safety events adjudication

Adjudication will be performed by experts independent of sponsor for the evaluation of whether deaths, cardiovascular SAEs and respiratory SAEs meet criteria for cardiovascular assessment endpoints. A confirmatory adjudication will occur for AECOPD exacerbations. Adjudicators will adjudicate these events in a consistent and unbiased manner throughout the study.

The goal of the adjudication is to ensure that all events reported by the site are judged uniformly, using pre-specified criteria by a group independent of the Sponsor. Adjudication Committee members will be blinded to treatment allocation. Adjudication Committee members' responsibilities and the process for data review are described in the AC Charter/Manual of Operation.

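### The TEAE Cox model censors event-free participants at last dose + 98 days with no cap at the analysis cut-off, last contact or death, so some unobserved time is counted as event-free

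*SAP*

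**What the plan says.** SAP 2.4.5.1 plans Cox hazard ratios for the TEAE overview table, common TEAEs, and AESIs and other selected groupings. Its censoring rule is: "Participants without an event will be censored at the end of the treatment-emergent period in the Cox model".

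SAP 2.1.4 defines that period. "The treatment-emergent adverse event period will include both" the treatment and residual treatment epochs, and the residual epoch runs from "the last administration of the IMP +15 days to the last administration of the IMP + 98 days". Protocol 9.4.2 agrees: "first administration of study medication to the last administration of the IMP +98 days". Neither definition is shortened for data cut-off, study withdrawal or death.

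SAP 2.4.5 limits the data: "All safety data collected up to the primary analysis cut-off date" are included, and that date is either the interim cut-off or the date the last patient completes Week 52. Under SAP section 4, a positive interim makes that lock the primary analysis for all endpoints.

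Elsewhere the SAP does write the truncation. The primary endpoint (SAP 2.4.4.1) ends observation at the earlier of last contact and the planned end of 52 weeks. The efficacy time-to-event estimand (Appendix L) censors at study discontinuation. In SAP 2.1.4, loss to follow-up ends the on-study observation period but is not mentioned for the treatment-emergent period.

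**The concern.** The censoring date and the data limit do not fit together. SAP 2.4.5 decides which events can be counted, but it does not move the date to which an event-free patient is kept at risk. If last dose + 98 days falls after the cut-off, or after the patient has left the study, the patient stays in the risk set over days when no event could have entered the database.

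At stake are the descriptive safety hazard ratios. Time at risk is overstated in both arms. If the arms differ in how much of it is unobserved, for instance through unequal withdrawal, the ratio is biased towards making the arm with more unobserved time look safer.

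**Working it through.** **Reproducing the plan's dates.** The protocol schedule of activities says "Last dose will be given at Week 50". Week 50 is Day 50 × 7 + 1 = 351, and 351 + 98 = Day 449. That is the Week 64 target day in the SAP visit-window tables, so the definition reproduces exactly. Week 52 is Day 365. A patient at Week 52 on the cut-off date, dosed through Week 50, is therefore credited with 449 − 365 = 84 days beyond the data. A patient still on treatment at the interim and dosed to date is credited with about 84 to 98.

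**Patients affected at the interim.** Inputs from the documents: follow-up fraction 0.92 (SAP section 3), 52-week treatment, last dose + 98 days. Assumptions not in the documents: uniform accrual over A years, dosing to date, no withdrawal, constant rate of 0.6 per year for a first event.

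If the last patient is x years short of Week 52 at the cut-off, the missing follow-up fraction is x²/(2A). Setting it to 0.08 gives x = √(0.16A).

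- Share of all patients less than 64 weeks from randomisation: (x + 12/52)/A.
- Share who are also event-free: [exp(−0.6(1 − x)) − exp(−0.6 × 64/52)]/(0.6A), with exp(−0.6 × 64/52) = 0.4778.

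| A (years) | x | all patients | event-free only | excess at-risk time |
|---|---|---|---|---|
| 1 | 0.400 | 63% | (0.6977 − 0.4778)/0.6 = 37% | 10.0% |
| 2 | 0.566 | 40% | (0.7706 − 0.4778)/1.2 = 24% | 6.8% |
| 3 | 0.693 | 31% | (0.8317 − 0.4778)/1.8 = 20% | 5.6% |

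The relevant column is event-free only, because the rule applies to no one else. A separate run gave 19% to 35% of patients and about 5% to 9% excess time, so the calculations agree closely.

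**Excess time, shown for A = 2.** Up to Week 50 the unobserved credit averages about 91 days (0.25 year). From Week 50 to Week 64 it falls from 14/52 year to zero.

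- Excess: 0.25 × (0.7706 − 0.5616)/0.6 + 0.5 × (14/52)² × 0.532 = 0.087 + 0.019 = 0.106.
- Observed at-risk time: 1.203 × (1 − 0.4778)/0.6 for those past Week 64, plus (0.797 − 0.488)/0.6 for the rest, = 1.047 + 0.514 = 1.561.
- Ratio: 0.106/1.561 = 6.8%.

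**Other conditions.**

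- Fraction 0.96, A = 2: x = √(0.08 × 2) = 0.4, so (0.6977 − 0.4778)/1.2 = 18% of patients, with about 4.7% excess time.
- A rarer event (0.1 per year) with 5% withdrawal per arm, simulated at fraction 0.92: 34% to 65% of all patients, with or without an event, have last dose + 98 days after their last observed day. Between 6.7% and 11.7% of credited time is unobserved.
- The same simulation at the Week 52 cut-off: 12% to 27% of patients and 1.8% to 3.1% of credited time.

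**Hazard ratio (simulations, 462 per arm, interim, 2-year accrual).**

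| Withdrawal | Capped rule | Rule as written |
|---|---|---|
| 10% in each arm, true HR 1.0 | 0.989; 1.001 | 0.989; 1.001 |
| 10% in each arm, true HR 1.5 | 1.502 | 1.497 |
| 15% placebo, 5% dupilumab, true HR 1.0 | 1.003; 0.995 | 1.025; 1.018 |
| 5% placebo, 15% dupilumab, true HR 1.0 | 0.987; 0.995 | 0.965; 0.971 |

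Paired entries are for 0.1 and 1.0 events per year. A further simulation with 20% against 10% withdrawal moved the ratio from 1.28 to 1.31. That is ln(1.31/1.28) = 0.023 on the log scale. With about 45% of 924 patients having an event (416), the standard error is roughly √(4/416) = 0.098, so the shift is about a quarter of one standard error.

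**The case against.** The strongest reply is that the SAP is silent on a cap and does not direct anyone to censor past the data. SAP 2.4.5 governs 2.4.5.1 and limits safety analyses to data up to the cut-off. SAP 2.1.4 presents the epochs as parts of an observation period. A sensible programmer would truncate at the last observed day. It is fair that the SAP does not say it intends to censor beyond the cut-off, and a reader should not infer that it does. But a censoring date is stated, it is the only one given for this model, and the SAP spells out truncation where it wants it. Followed literally, the rule gives the wrong date.

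Three limits on scope stand in full.

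- It is tempting to say that everyone not past Week 64 at the cut-off is affected. That is false. The protocol asks patients who stop treatment early to stay in the study. One whose last dose was at Week 10 and who is at Week 40 has a treatment-emergent period ending at Week 24, fully observed. Patients with an event are not censored at all.
- Fraction 0.92 is the lowest in SAP Table 9. The effect shrinks at later fractions and is small at the Week 52 cut-off.
- A reader might infer that Kaplan-Meier incidence and exposure-adjusted rates are understated. If the same times were used, they would be: one simulation gave Week 52 incidence falling from 44.9% to 42.2%. But the rule is confined to the Cox model, and the SAP does not say that its times feed anything else.

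It is also fair that no decision hangs on this. SAP 2.4.5 calls the safety analysis essentially descriptive with no systematic testing, risk differences are reported beside the hazard ratios, and later data are reported in a CSR addendum or at a later lock.

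**Conclusion.** The rule is wrong as written, and the consequence is minor. For event-free patients whose last dose + 98 days falls after the cut-off or after they leave the study, unobserved time is counted as event-free.

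At an interim at fraction 0.92 this reaches about a fifth to somewhat over a third of patients and adds about 5% to 10% to at-risk time. It adds about 3% or less at the Week 52 cut-off. These figures rest on uniform accrual over 1 to 3 years and, for the interim, on dosing to date and 0.6 events per year. None of these is in the documents, and a rarer event raises the affected share.

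The documents do not support a claim that the safety comparison is materially biased. The hazard ratio is essentially unchanged with equal withdrawal. The 2% to 3% shift needs an assumed imbalance (20% against 10%, or 15% against 5%) for which the documents give no figure. No type I error is involved.

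**What to change.** In SAP 2.4.5.1, censor event-free participants at the earliest of last IMP + 98 days, last contact date or death, and the analysis cut-off date. State that the same rule applies to the TEAE Kaplan-Meier estimates and exposure-adjusted rates, for which no censoring rule is now given.

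The cost is one clause in the SAP. It needs no new data and changes no study procedure.
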